9 ADVERSE EVENTS (AE) AND SERIOUS ADVERSE EVENTS (SAE)

9.1 Safety Assessments

Throughout the study, subjects will be monitored for signs and symptoms of AEs. An AE can be any unfavorable and unintended sign (including an abnormal laboratory finding, for example), symptom, or disease temporally associated with the use of a medicinal (investigational) product, whether or not considered related to the medicinal (investigational) product. This definition includes the worsening of a pre-existing condition, the development of investigational product dependency, and suspected investigational product-drug interactions.

Adverse events will be collected for all untoward medical occurrences in a subject entered into this clinical trial (as defined by the study protocol) whether or not a pharmaceutical product has been administered.

An SAE is an AE that meets one or more of the following criteria:

- Results in death (including reports of death with no specific AE identified, i.e., "death only" reports)
- Results in a persistent or significant incapacity or substantial disruption of the ability to conduct normal life functions
- Is life-threatening
- Requires inpatient hospitalization or prolongation of existing hospitalization
- Results in persistent or significant disability/incapacity
- Is a congenital anomaly/birth defect
- Is an important medical event that may not fall into one of the above categories but may jeopardize the subject and may require medical or surgical intervention to prevent one of the outcomes above

An *Unexpected AE* is any treatment-related AE that is not identified in nature, severity, or frequency in current literature on the test product (i.e., Investigators Brochure).

9.1.1 Method of Detecting AEs and SAEs

Care will be taken not to introduce bias when detecting AEs and/or SAEs. Open-ended and non-leading verbal questioning of the subject is the preferred method to inquire about AE occurrence.

Appropriate questions include:

- "How are you feeling?"
- "Have you had any (other) medical problems since your last visit/contact?"
- "Have you taken any new medicines, other than those provided in this study, since your last visit/contact?"

Page 41 of 65

9.2 Reporting Requirements

9.2.1 Serious and/or Unexpected Adverse Events

Any serious or investigational product-related unexpected AE occurring in this study must be reported to the Medical Monitor/Brickell Biotech immediately upon awareness of the event per the following:

A SAE form must be completed by the investigator and **faxed to [contact] or email at [contact]**. At the time of the initial report the following information should be provided at a minimum: subject identifiers, adverse event description, event status and severity, onset date, date the Investigator learned of the event, criteria for classification of the event as serious, disposition of the subject and Investigator assessment of the association between the event and study drug.

The investigator will keep the original of this SAE form on file at the study site. When the Investigator becomes aware of significant new information regarding an ongoing serious adverse event, a follow-up report should be promptly **faxed to [contact] or email at [contact]**. When the investigator determines that there is no more information likely to be available, a final report should be provided.

9.2.2 Adverse Event Reporting

All AEs, including SAEs and treatment-related unexpected AEs, must be recorded by the investigator on the standard AE form. The investigator will be required to describe the AE, onset and stop date, severity, the course of action taken, if any, relationship to the study drug as well as any pertinent data necessary to allow a complete evaluation of the AE. For SAEs, an additional report must be completed (this form will be provided in the Investigator Site Binder).

A clinical determination of the intensity of an AE will be completed using the following definitions as guidelines:

Mild:	Awareness of sign or symptom, but easily tolerated
Moderate:	Discomfort enough to cause interference with usual activity
Severe:	Incapacitating with inability to work or do usual activity

The investigator must determine the relationship of the AE to the test article according to the following categories:

Definitely Related	An event that follows a reasonable temporal sequence from administration of the test article; that follows a known or expected response pattern to the test article; and that is confirmed by improvement on stopping or reducing the dosage, and reappearance of the event on repeated exposure (re-challenge).
Probably Related	An event that follows a reasonable temporal sequence from administration of the test article; that follows a known or expected response pattern to the test article; and that is confirmed by improvement on stopping or reducing the dosage of the test article; and that is unlikely to have been caused by concurrent/underlying illness or other drugs, procedures, or other causes.
Possibly Related	An event that follows a reasonable temporal sequence from administration of the test article; that follows a known or expected response pattern to the test article; but may have been caused by concurrent/underlying illness, other drug, procedure, or other causes.
Unlikely Related	An event that does not follow a reasonable temporal sequence from administration of the test article; that does not follow a known or expected response pattern to the test article, or most likely was caused by concurrent/underlying illness, other drug, procedure, or other causes, because of their known effects.
Not Related	An event almost certainly caused by concurrent/underlying illness, other drug, procedure, or other causes.

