^[2] P-values comparing active dose to vehicle are based on an ANCOVA model for change scores, with covariate adjustment for the baseline value.

Reference: Listing #(s)

Path\filename.sas ddmmmyyyy hh:mm

Programming Notes: Repeat for Table 14.2.5.2 DLQI Change Score ANCOVA (PP Population)

Brickell Biotech, Inc.
BBI-4000-CL-203

Database Date/Analysis: DDMMYYYY/Draft
Page x of y

Table 14.3.1.1
Overall Summary of Treatment-Emergent Adverse Events
Safety Population
Part 1 of 2

	Vehicle (N=)	BBI-4000 5% (N=)	BBI-4000 10% (N=)	BBI-4000 15% (N=)
Total Number of TEAEs	xx	xx	xx	xx
Total Number of TESAEs	xx	xx	xx	xx
Number (%) of Subjects Reporting at Least One:				
TEAE	n (x.x%)	n (x.x%)	n (x.x%)	n (x.x%)
TEAE by Severity ^[1]				
Mild	n (x.x%)	n (x.x%)	n (x.x%)	n (x.x%)
Moderate	n (x.x%)	n (x.x%)	n (x.x%)	n (x.x%)
Severe	n (x.x%)	n (x.x%)	n (x.x%)	n (x.x%)
TEAE by Relationship ^[2]				
Not Related	n (x.x%)	n (x.x%)	n (x.x%)	n (x.x%)
Related	n (x.x%)	n (x.x%)	n (x.x%)	n (x.x%)
TEAE Leading to Discontinuation of Study Drug	n (x.x%)	n (x.x%)	n (x.x%)	n (x.x%)
TEAE Requiring Dose Interruption of Study Drug	n (x.x%)	n (x.x%)	n (x.x%)	n (x.x%)
TEAE Requiring Dose Reduction of Study Drug	n (x.x%)	n (x.x%)	n (x.x%)	n (x.x%)
TEAE Leading to Premature Withdrawal from the Study	n (x.x%)	n (x.x%)	n (x.x%)	n (x.x%)
TEAE Causing Death	n (x.x%)	n (x.x%)	n (x.x%)	n (x.x%)
Treatment Area				
TEAE in Treatment Area?	n (x.x%)	n (x.x%)	n (x.x%)	n (x.x%)

Abbreviations: SAE, serious adverse event; TEAE, treatment-emergent adverse event; TESAE, treatment-emergent serious adverse event

^[1] Subjects reporting more than one adverse event are counted only once using the highest severity.

^[2] Subjects reporting more than one adverse event are counted only once using the closest relationship to study drug. Not related events includes those reported as “Unlikely” or “Not Related” to study drug; related events include those reported as “Possibly Related,” “Probably Related,” or “Definitely Related” to study drug.

Reference: Listing #(s)

Path\filename.sas ddmmmyyy hh:mm

Programming note: Table continues on next page.

Table 14.3.1.1
Overall Summary of Treatment-Emergent Adverse Events
Safety Population
Part 2 of 2

	Vehicle (N=)	BBI-4000 5% (N=)	BBI-4000 10% (N=)	BBI-4000 15% (N=)
TESAE	n (x.x%)	n (x.x%)	n (x.x%)	n (x.x%)
TESAE by Severity ^[1]				
Mild	n (x.x%)	n (x.x%)	n (x.x%)	n (x.x%)
Moderate	n (x.x%)	n (x.x%)	n (x.x%)	n (x.x%)
Severe	n (x.x%)	n (x.x%)	n (x.x%)	n (x.x%)

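### Protocol 9.2.2 requires a known or expected response pattern for every related grade, so a non-serious reaction outside any such pattern cannot be rated related or trigger the unexpected-AE report

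*Protocol*

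**What the plan says.** Protocol 9.2.2 makes the scale binding: "The investigator must determine the relationship of the AE to the test article according to the following categories". By contrast, the intensity definitions just above it are offered only as guidelines. There is no grade for events that cannot be assessed. The five rows are:

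- **Definitely Related**: plausible timing, and the event "follows a known or expected response pattern to the test article; and that is confirmed by improvement on stopping or reducing the dosage, and reappearance" on re-exposure.
- **Probably Related**: plausible timing, the same pattern clause ("expected response pattern to the test article; and that is confirmed by improvement on stopping or reducing the dosage of the test article"), with other causes unlikely.
- **Possibly Related**: plausible timing, and an event "that follows a known or expected response pattern to the test article; but may have been caused by concurrent/underlying illness" or another factor.
- **Unlikely Related**: implausible timing, followed after a semicolon by an event "that does not follow a known or expected response pattern to the test article, or most likely was caused by" something else.
- **Not Related**: another cause is almost certain.

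Protocol 9.1 says an Unexpected AE "is any treatment-related AE that is not identified in nature, severity, or frequency in current literature on the test product", meaning the Investigator's Brochure. Protocol 9.2.1 then states: "Any serious or investigational product-related unexpected AE occurring in this study must be reported to the Medical Monitor/Brickell Biotech immediately".

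In the SAP, footnote 2 of Table 14.3.1.1 reads "Not related events includes those reported as" Unlikely or Not Related; Possibly, Probably and Definitely form the Related row. Each subject is counted once, at the closest relationship. Tables 14.3.1.4 and 14.3.1.6 show related events only. The shells for Listing 16.2.7.1 and Tables 14.3.2.2 and 14.3.2.3 carry four causality levels (Not, Unlikely, Possibly, Related), not five.

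**The concern.** The protocol sets up an immediate-report route for non-serious reactions that are new in kind, then makes entry to it depend on a relatedness rating that the causality scale withholds from exactly those reactions.

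Prompt notice has value here. Safety and local tolerability are a primary objective (Protocol 3.1), and treatment-related AEs are a specified output (Protocol 10.4). The protocol says the isopropyl myristate gel was first used clinically in study CL-103: 14 days, healthy subjects, 10 on 5% and 10 on 15%. In that study the 15% gel gave a Day 14 Cmax of 11.2 ng/mL against 2.39 ng/mL for the old 15% formulation (11.2 / 2.39 = 4.7-fold). The AUC was 119 against 30.9 hr.ng/mL (119 / 30.9 = 3.9-fold), and there were 26 AEs against 9. The present trial doses for 42 days with no data monitoring committee planned (SAP 7.4.6.3).

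**Working it through.** The plan gives no figure to reproduce, so the check is of the definitions against each other.

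**Step 1. Write 9.2.2 as conditions.** Let T = plausible timing, K = known or expected pattern, D = improvement on stopping or reducing, R = reappearance on re-exposure (each yes or no). Let A = other cause: none, may, most likely, almost certain.

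| Row | Condition |
|---|---|
| Definitely | T and K and D and R |
| Probably | T and K and D and A = none |
| Possibly | T and K and A at least may |
| Unlikely, criteria as alternatives | not T, or not K, or A at least most likely |
| Unlikely, first two criteria joint | (not T and not K), or A at least most likely |
| Not Related | A = almost certain |

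There are 2 × 2 × 2 × 2 × 4 = 64 combinations.

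**Step 2. Take events outside any known pattern (not K).** There are 64 / 2 = 32. K is a condition of all three related rows, so 0 of 32 reach one.

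**Step 3. Keep those with plausible timing.** There are 32 / 2 = 16.

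- Unlikely read as alternatives: all 16 meet it.
- First two criteria read jointly: only the two upper levels of A qualify, 2 × 2 × 2 = 8. The other 8 fit no row, because Not Related needs an almost certain other cause.
- If timing is required and the final or joins only the last two criteria, none of the 16 meets Unlikely. Only the 2 × 2 × 1 = 4 with an almost certain other cause have a row (Not Related).

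The critical case, good timing and no other cause, is Unlikely under the first reading and has no row under the other two.

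**Step 4. Follow it through.** Not related means not an Unexpected AE (9.1), and so, if non-serious, no immediate report (9.2.1). If rated Unlikely, the event counts toward the Not Related row of Table 14.3.1.1, unless the same subject also has a related event. It is absent from Tables 14.3.1.4 and 14.3.1.6.

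**Step 5. Remove only the pattern clause from the related rows.** Possibly then takes 2 × 2 × 3 = 12 of the 16 and Probably takes 2 more (A = none, D = yes), giving 14 of 16. Of these, 8 have a most likely or almost certain other cause and also satisfy Unlikely on that ground (first or second reading), so 14 − 8 = 6 become related without overlap. The 2 left over have no other cause and no improvement on stopping or reducing.

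**Step 6. The same hole for typical events.** With T and K satisfied, A = none and D = no, the event fails Definitely and Probably on D, Possibly on A, and Unlikely and Not Related on every reading. A mild dry mouth with dosing continued and no other explanation is such a case.

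These are counts of logical combinations. They say nothing about how often each occurs.

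**The case against.** The strongest reply is that known or expected response pattern is nowhere defined. Protocol 9.1 judges unexpectedness against the Brochure, whereas 9.2.2 does not tie pattern to the Brochure, and the risk sections describe an open-ended anticholinergic profile. An unlisted effect that fits class pharmacology can therefore be in pattern, rated related, and still unexpected, so the 9.2.1 trigger fires. Events unexpected only in severity or frequency can also still qualify. This stands. A reader might infer that no unexpected reaction can ever be rated related or reported; the documents support that only for non-serious reactions outside every expected pattern.

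Three further inferences also fail.

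- **That these events are tabulated as Not Related throughout the related-event tables.** Only Table 14.3.1.1 has such a row. Tables 14.3.1.4 and 14.3.1.6 would omit the event, and Table 14.3.1.8 covers serious events only.
- **That the signal is lost.** All TEAEs appear by arm by system organ class, preferred term and severity, whatever the causality. Local tolerability is scored without a causality rating. Serious events are reported immediately regardless of cause, and the sponsor is told of early discontinuations as soon as possible (Protocol 7.4).
- **That the share of related TEAEs in CL-201 (66.7%) measures the effect.** It does not show how many events were out of pattern, and the documents do not say that CL-201 used this scale. They describe the systemic events of earlier studies as consistent with the class, so the number affected may be small.

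An investigator may also rate by judgement despite the wording. That would soften the effect but make ratings depend on the site.

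**Conclusion.** The conflict between 9.2.2 and the nature limb of 9.1 and 9.2.1 is real on the literal text, and nothing elsewhere in the protocol or SAP overrides it. It is confined to non-serious reactions outside any known or expected pattern, class pharmacology included, and affects two things: the related/not-related split and immediate notification. The conclusion assumes that sites apply the mandatory rows as worded; where an event with good timing and no other cause ends up depends on how the Unlikely row is parsed. The number of events cannot be estimated from the documents. The gap for typical events with dosing continued does not depend on the meaning of pattern. This is a wording correction that should be made, not a threat to the trial's main conclusions.

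**What to change.** In Protocol 9.2.2:

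1. Make a known or expected pattern supporting evidence, not a requirement, for Possibly and Probably Related.
2. Word Possibly so that it also covers an event with a reasonable temporal sequence and no more likely other cause. This closes the gap in step 6 and the two leftover combinations in step 5.
3. Delete absence of pattern as a ground for Unlikely, and punctuate the row so that implausible timing or a more likely other cause each suffices.

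In the SAP, give the shells for Listing 16.2.7.1 and Tables 14.3.2.2 and 14.3.2.3 the protocol's five levels, which the footnote of Table 14.3.1.1 already uses.

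Possibly should not be widened to every event whose causal link cannot be excluded. With nightly dosing for 42 days most on-treatment events have plausible timing, and the grade would stop discriminating.

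The cost is a change to one protocol table, the matching CRF guidance and three SAP shells. The downside is more events rated Possibly Related in all arms, vehicle included.

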9.2.3 Pregnancy

Sexually active females of childbearing potential (FOCBP)* must have a negative pregnancy test prior to study enrollment and must use an effective method of contraception during the course of the study, in a manner such that risk of failure is minimized. Prior to study enrollment, FOCBP must be advised of the importance of avoiding pregnancy during trial participation and the potential risk factors for an unintentional pregnancy. The subject must sign an informed consent form documenting this discussion.

FOCBP must agree to periodic pregnancy testing and use a medically acceptable method of contraception while receiving protocol-assigned product. This includes perimenopausal women who are less than 12 months from their last menses. Acceptable contraceptive methods include the following:

- Abstinence for the duration of the study or where partner is sterile (e.g., vasectomy) is acceptable form of contraception
- Hormonal contraception, including oral, injectable, or implantable methods started at least 2 months prior to screening, OR
- Two forms of non-hormonal contraception, including intrauterine devices (at least 1-week status post placement), or properly used barrier methods (e.g., male or female condoms, cervical cap/diaphragm, spermicidal agents, etc.).

^{*} Females of childbearing potential for this study includes any female 18 years of age or older who has not undergone successful surgical sterilization (hysterectomy, bilateral tubal ligation (at least

Page 43 of 65

six months prior to baseline) or bilateral oophorectomy) or is not postmenopausal (defined as amenorrhea greater than 12 consecutive months in women 55 years or older).

Subjects who become sexually active or begin to have relations with a partner who is not sterile during the trial must agree to use an effective form of birth control for the duration of the study.

9.2.3.1 Time period for collecting pregnancy information

FOCBP should be instructed to contact the investigator immediately if they suspect they might be pregnant (e.g., missed or late menstrual period). If a subject or investigator suspects that a subject may be pregnant at any time during the study the investigational product must be withheld until the results of laboratory pregnancy testing are available. If pregnancy is confirmed, the subject must not receive or apply further investigational product and must be discontinued from the study.

9.2.3.2 Action to be taken if pregnancy occurs

If following initiation of investigational product, it is subsequently discovered that a trial subject was pregnant or may have been pregnant at the time of test article exposure, the investigator must immediately notify the Medical Monitor of this event, and record the pregnancy on the appropriate pregnancy surveillance form. The form will be sent to the Medical Monitor by fax or email as listed on the title page of the protocol. The investigator must notify the IRB of any pregnancy associated with the study therapy and keep careful source documentation of the event.

Protocol-required procedures for those subjects that are discontinued from the study must be performed on the subject unless contraindicated by pregnancy (e.g., x-ray studies). Other appropriate pregnancy follow-up procedures should be considered if indicated, including counseling of the subject by the investigator and her managing physician or health care provider (e.g., obstetrician). In addition, the investigator must report to the Medical Monitor, on the appropriate pregnancy surveillance form(s), any follow-up information regarding the course of the pregnancy, including perinatal (period immediately before and after birth) and neonatal (infants up to 28 days after birth) outcome.

Although pregnancy itself is not an AE, any complications during pregnancy should be recorded as AEs (or SAEs – if they fulfill the SAE criteria). **Offspring will be followed for a minimum of eight weeks.** Any congenital anomaly/birth defect in a child born to a subject exposed to the test article(s) will be recorded as a SAE and details documented in the pregnancy surveillance form. An abortion, whether accidental, therapeutic or spontaneous will be reported as a SAE.

9.2.4 Follow-up and Final Reports

Subjects who have had a SAE must be followed clinically until all parameters, including laboratory values, have either returned to normal or are otherwise explained. If death was the outcome of the event on the initial SAE Report, a Follow-up/Final Report, including autopsy report, when performed, must be completed.

Subjects who report a pregnancy during the treatment phase of the study will be followed until pregnancy resolution and information regarding the health status of the infant will be collected.

Page 44 of 65

9.3 Procedures for Unblinding of Investigational Product

The sponsor will break the blind for subjects only if the medical monitor in conjunction with the Sponsor deems that a conclusion regarding the progression of the study, as planned, cannot be made based on the blinded data.

In addition, when necessary for the safety and proper treatment of a subject, the investigator may unmask the subject's investigational product assignment to determine and institute appropriate care, and subsequently the subject will be discontinued from receiving treatment. When possible, the Sponsor should be notified prior to unmasking. To break blind, the investigator or a designee will scratch off the blind break area (see Section 5.1) on the label panel adhered to the subject record at the time of dispensing the investigational product. In the event of a premature breaking of the randomization code, the reason for breaking the code will be recorded in the subject's source documents

10 STATISTICAL PROCEDURES

A detailed statistical analysis plan will be generated prior to the final database lock. Database lock will precede unblinding and follow completion of data entry, verification and validation, database audit, and data clarification resolution.

10.1 Analysis Populations

Subjects will be classified into the Safety, Intent-to-Treat (ITT), and Per-Protocol (PP) patient sets according to the following definitions.

Safety Patient Set

The Safety Patient Set will include all subjects randomized in the study who received study drug at least once. Subjects will be included in the treatment group based on the majority of actual treatment they received (even if not the treatment group to which they were randomized).

ITT Population

The ITT Patient Set will include all subjects who were randomized and dispensed study drug. Subjects will be included in the treatment group to which they were randomized, regardless of the treatment received.

PP Population

The PP Patient Set will be a subset of the ITT Patient Set and will include subjects who meet the following criteria:

- Meets the inclusion/exclusion criteria
- Has not taken or applied any interfering concomitant medications.
- Completed the following visits:
 - o Visit 2 GSP 1, and the required GSP data collection
 - o Visit 3 GSP 2, and the required GSP data collection
 - o Visit 4 Re-screening GSP 3, and the required GSP data collection
 - \circ Visit 11(GSP 4) Day 41 (\pm 2 days), and the required GSP data collection
 - \circ Visit 12 (GSP 5) Day 42 (\pm 2 days), and the required GSP data collection

Page 45 of 65

 \circ Visit 13 (GSP 6) Day 43 (\pm 2 days), and the required GSP data collection

Subjects will be included in the treatment group based on the treatment received.

